## Summary

We will perform a 2 year double blind, placebo controlled trial of doxycycline in 40 patients with LAM. The main endpoints will be change in FEV1, other measures of efficacy, safety and dose required to suppress MMP activity. After clinical evaluation, lung function, shuttle walk, QoL assessment, blood tests, serum and urine MMPs (termed full assessment) plus baseline chest X-ray patients will be randomised to doxycycline 50 mg od or placebo. Patients will be assessed at 2 weeks for a safety screen, every 3 months for clinical evaluation and spirometry and at 12 and 24 months for full assessment. At 1, 2 and 3 months urine zymography will be performed to see if MMPs are present in urine at the prescribed dose. Doxycycline will be increased to 50mg bd then 100 mg bd at monthly intervals up to three months after urine zymography has been performed. To avoid withholding treatment from those who decline rapidly, patients who, on two occasions, have either a fall from baseline FEV1 of 300 ml or fall in resting SaO2 of 3% will be assessed by an independent expert ([name]). Patients receiving placebo will be given the option of doxycycline according to protocol. Those receiving doxycycline the option of continuing in the study or withdrawal. These patients and those withdrawn due to recurrent pneumothorax, increase in chylous effusion or bleeding angiomyolipoma will be included in a composite safety endpoint and analysed on an intention to treat basis. Power calculations based on retrospective cohorts show that 20 patients per group will give 80% power to detect a 70 ml/year difference in FEV1 based an assumed SD for a fall in FEV1 of 75 ml/year. The mean slope of regression lines for FEV1 and FVC, plus change DLCO, shuttle walk distance and QoL in the doxycycline and placebo groups will be compared by parametric or non-parametric analysis dependent on data, time to composite safety endpoint by Kaplan-Meier analysis, complications and adverse events by Chi Square test.

## Introduction

### Lymphangioliomyomatosis

Lymphangioliomyomatosis (LAM) is a disease of the lungs and lymphatics, which can occur sporadically or in association with tuberous sclerosis complex (TSC). The disease is rare, occurring in 1-2 / million of the population but in up to 40% of women with TSC LAM almost exclusively affects women, generally developing before the menopause. The disease is characterised by progressive pulmonary cystic change, recurrent pneumothorax, chylous pleural collections and, in most cases, progressive respiratory failure. Abdominal manifestations caused by obstruction and dilation of the axial lymphatics include lymphadenopathy, cystic lymphatic masses (lymphangioliomyomas), chylous ascites and angiomyolipoma (a benign tumour). Survival in LAM is, 70 90% at 10 yrs, although this is highly variable since long-term survivors have been described. Diagnosis is made by a combination of clinical features and computed tomography scanning or, in cases of doubt, lung biopsy. In patients with rapidly progressive disease, hormone treatment (predominantly progesterone) has been used, although no firm evidence supports its use. Otherwise, treatment is aimed at complications including pneumothorax, chylous collections and extra-pulmonary manifestations. The only treatment for severe LAM is currently lung transplantation.

Recently identification of abnormalities in the tuberous sclerosis complex (TSC) genes in sporadic and TSC associated LAM have identified dysregulation of the mTOR pathway in LAM and have lead to clinical trials of mTOR inhibitors such as rapamycin in LAM and TSC. At the time of writing these have not been reported but appear promising.

#### Background and preliminary data

Cystic lung destruction is the hallmark of pulmonary LAM and generally results in respiratory failure over a variable period of time. Over-activity of proteases including elastase, trypsin and the matrix metalloproteinases (MMPs) is responsible for parenchymal destruction in emphysema and other lung diseases. The MMPs are a family of zinc dependent proteolytic enzymes with proteolytic activities against extra-cellular matrix proteins. The MMPs are overexpressed in inflammatory and neoplastic diseases where in addition to processing extra-cellular matrix they also have roles in metastasis, angiogenesis, growth factor activation and inactivation. MMPs -1, -2, and -9 are involved in the sequential digestion of collagen and gelatin and are strongly expressed in the walls of cysts where it is thought they contribute to parenchymal destruction in LAM. Further, MMPs can be detected by gelatin zymography in the urine of patients with LAM but not controls. Doxycycline is a tetracycline antibiotic in common clinical use. In addition to its antimicrobial action it inhibits the synthesis and activity of several MMPs and inhibits proliferation of a range of cell types including arterial smooth muscle, cancer cells and cancer model systems. In preliminary experiments we have demonstrated that primary LAM derived and angiomyolipoma cells produce MMP-2 and -7 and that MMP expression and proliferation in these cells is inhibited by doxycycline.

#### Specific issues in orphan disease clinical trials and rationale for trial design

Studying orphan diseases presents specific challenges, specifically the limited number of patients available, wide geographic distribution and low priority for funding due to the perceived poor economic benefit. Patients are well informed about potential developments due to patient groups and internet based information and may obtain potential treatments 'off label' making definitive research studies impossible. As LAM is rare, cohorts drawn from a wide area are required for studies to achieve adequate power. We have 15 years experience of LAM research and from our UK LAM database estimate there are approximately 120 patients in the UK. We are currently performing an open label study of Sirolimus in LAM and tuberous sclerosis (TESSTAL, a Study of **The Efficacy and Safety of Sirolimus (Rapamycin) Therapy for Renal Angiomyolipomas in Patients with Tuberous Sclerosis Complex And Sporadic Lymphangiomyomatosis**). This included six patients with LAM whom we found to be well motivated and will travel

long distances for study visits (including Cornwall, Kent and Perth). Despite the known adverse effects of rapamycin six of eight eligible (i.e. with LAM and angiomyolipoma) patients invited took part in the study. The current study protocol has been designed as a simple protocol which is both inclusive of most patients with LAM and has a follow up which is similar to routine clinical care which we hope will facilitate recruitment. In addition the protocol is less demanding than that of the TESSTAL study. As most patients are known to us via our database or clinical contacts we expect recruitment to be complete within six months.

Designing a definitive study is difficult without having an estimate of the likely size of effect, if this is large, as suggested by the one case report a small number of patients are needed. If it is small as seems more likely *a priori*, a larger number of patients are needed requiring European collaboration and considerably greater funding. We therefore designed a pragmatic pilot study using a single geographic population with a simple, inexpensive protocol which will serve several functions, specifically to: (1) determine the optimum dose of doxycycline needed to suppress MMP production. (2) define the safety profile of doxycycline in LAM. (3) provide evidence of efficacy and size of effect. (4) provide data to help optimise the design and logistics of future trials.

## **2 Study aims/objectives**

### Hypothesis

Doxycycline will prevent matrix metalloproteinase dependent tissue destruction in lymphangioleiomyomatosis (LAM) thus preserving lung function, exercise capacity and quality of life.

We will perform a randomised placebo controlled trial of doxycycline on rate of decline of FEV1 over two years against matched placebo. This study will:

- (1) determine the optimum dose of doxycycline needed to suppress MMP production.
- (2) define the safety profile of doxycycline in LAM.
- (3) provide evidence for efficacy and size of effect.
- (4) provide data to help optimise the design and logistics of future trials.

With the data obtained we will be in a strong position to apply for European funding for a European wide trial should this still be required.

## **3 Investigational plan**

### Patient population and recruitment

Forty patients with either sporadic LAM or TSC-LAM will be recruited from the UK LAM database, physician referrals, LAM Action (a patients group for women with LAM) and the Tuberous Sclerosis Association. Patients will be contacted by mail by the principal

investigator. Potential participants will receive a preliminary information sheet and response sheet for return by prepaid post. Those that express a potential interest in participating will be offered a face to face interview with one of the study doctors to assess eligibility, answer questions, obtain details of all physicians involved in their care and obtain written consent prior to enrolment. We anticipate recruitment will be complete within 12 months of starting the study.

#### *Inclusion Criteria*

- Sporadic LAM diagnosed either by cystic lung disease on HRCT classical of LAM plus angiomyolipoma or chylous effusion or cystic lung disease on HRCT and tissue biopsy showing LAM or angiomyolipoma
- TSC-LAM diagnosed by cystic lung disease on HRCT and tuberous sclerosis diagnosed by TSC consensus criteria.
- Patients with either an FEV1 below 80% predicted or evidence of a 20% deterioration in FEV1.
- Hormone and bronchodilator treatment for LAM\* is allowed providing treatment has not changed in the three months prior to enrolment.  
\* progesterone, GnRh agonists and bronchodilators.

#### *Exclusion criteria*

- Inability to give informed consent.
- Mental retardation.
- Age less than 18 years.
- Pneumothorax, chylous effusion, bleeding angiomyolipoma or change in hormone treatment within 3 months.
- Previous organ transplantation.
- Severe or uncontrolled epilepsy.
- Use of any oral contraceptive pill.
- Pregnancy or breast feeding. Pre-menopausal patients must be willing to use appropriate birth control measures to avoid pregnancy while enrolled in the study.
- Major systemic diseases (malignancy, myocardial infarction or unstable angina, type1 diabetes, severe hypertension, liver cirrhosis).
- Use of drugs known to interact with doxycycline, including anticoagulation with warfarin.
- Anticoagulation with warfarin.
- Hypersensitivity to tetracyclines.
- Treatment with mTOR inhibitor within the previous 3 months (sirolimus, everolimus).
- Use of doxycycline or other experimental drug within the previous three months.

#### Sample size

Power calculations have been based on several retrospective cohorts. In our UK national study the rate of decline in FEV1 for all patients was 118 ml/yr (SD=142, n=43) and 106 ml/yr (SD=143, n=57) in a similar French cohort. In a larger study of less severely affected patients from the NIH the overall yearly rate of decline in FEV1 was 75 ml/yr (SD=149, n=275). All of these studies have used data from retrospective series performed at different sites at different times. Using prospective standardised measurements performed by the same operators we expect the variation in change in FEV1 to be smaller than observed in these cohorts. Using 20 patients per group there will 80% power to detect a difference of 70 ml/year difference in FEV1 based on the assumption that the SD of the fall in FEV1 in the trial is 75 ml/year.

## Treatments/Interventions

### **Initial Assessment.**

After giving informed consent, patients will have a baseline evaluation at a screening visit. This will include a history and physical examination by one of the study doctors, full lung function, shuttle walk (with SaO2 monitoring), quality of life, FBC, U&E, LFT, glucose, calcium, serum MMP-2, -7, -9, urine zymography, serum for biomarkers and circulating LAM cell isolation (termed full assessment). In addition a baseline chest X-ray will be performed. All patients will have a pregnancy test.

### **Randomisation and initiation of doxycycline.**

Patients will be randomised to either doxycycline 50 mg od or matched placebo. Randomisation will be performed by the University of Nottingham Clinical Trial Support Unit (CTSU).

[figure not shown]
### **Two week safety screen.**

After two weeks of doxycycline treatment patients will have a safety screen comprising FBC, U&E, LFT, glucose, and amylase. A study phone call will be made to detect side effects and reinforce safety advice. Blood tests will be performed locally and sent to the centre in Nottingham.

### **Dose escalation of doxycycline and urine zymography.**

In order to determine the dose of doxycycline that suppresses MMP production doxycycline will be increased and urine MMPs measured. After one month doxycycline will be increased from 50mg od to 50mg bd, after two months to 50 mg tds and at three months to 100 mg bd. Patients will stay on this dose for the remainder of the study. Blinding will be maintained during dose adjustment by prescribing all patients four study tablets being a combination of 50mg doxycycline and matched placebo tablets, dose adjustment will be performed by an independent person in a double blind manner. At one, two and three months urine will be sent by post to the study centre and zymography will be performed by a person blind to the clinical details of the patient. The group has a longstanding interest in the biology of MMPs in respiratory disease and expertise in MMP analysis. In a preliminary study we have shown that urine MMPs are stable for greater than 30 hours at room temperature and can therefore be analysed at a site distant from collection (figure 1).

**Figure 1. Urinary MMPs in LAM.** Urine from three patients with LAM taking no treatment, rapamycin or doxycycline analysed by gelatin zymography after delays of 6-72 hours. MMPs are detectable in the urine of patients with no significant reduction up to 30 hours. The patient taking doxycycline has almost undetectable MMPs. LC-MMP-9: lipocalin associated MMP-9.

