### **Routine study assessments.**

Patients will be seen at the study centre every 3 months for clinical evaluation and spirometry (post bronchodilator). For safety purposes patients will have urinalysis, FBC, U&E, LFT, glucose, amylase and a pregnancy test. Patients with TSC will have a their epilepsy reviewed. At 12 and 24 months patients will undergo full assessment as described under initial assessment.

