### **Monthly phone contact.**

During months when no study visit is scheduled a telephone call will be made to participants to check compliance, reinforce safety advice and detect adverse events.

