# Flow chart

**Table2: Data capture summary**

Visit (months)	Screening	2 wk	1	2	3	6	9	12	15	18	21	24
History and exam	✓				✓	✓	✓	✓	✓	✓	✓	✓
Blood tests (1)	✓	✓			✓	✓	✓	✓	✓	✓	✓	✓
Urine zymography	✓		✓	✓	✓			✓				✓
Pregnancy test	✓				✓	✓	✓	✓	✓	✓	✓	✓
Serum MMPs	✓							✓				✓
Quality of life	✓							✓				✓
Urinalysis	✓				✓	✓	✓	✓	✓	✓	✓	✓
Chest X-ray	✓											
Spirometry	✓				✓	✓	✓	✓	✓	✓	✓	✓
Full lung function (2)	✓							✓				✓
Review of epilepsy (3)	✓	✓			✓	✓	✓	✓	✓	✓	✓	✓

A study phone call will take place at 2 weeks, 4, 5, 7, 8, 10, 11,13, 14, 16, 17, 19, 20, 22, and 23 months to ensure no problems have developed.

1. renal profile, liver profile, bone profile, glucose, thyroid function, amylase, full blood count and differential. 2. Spirometry, lung volumes, gas transfer and shuttle walk test with oxygen saturation. 3 only in patients with TSC.

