### Definitions

**Adverse event (AE)** : Any untoward medical occurrence in a patient which does not necessarily have a causal relationship with this treatment.

This includes “any unfavourable and unintended sign (including an abnormal laboratory finding), symptom or disease temporally associated with the study drug”. This may include, for example, a cold, or an accident.

**Adverse reaction to an investigational medicinal product (AR)**: all untoward and un-intended responses to an investigational medicinal product related to any dose administered.

All adverse events judged by either the reporting investigator or the chief investigator as having a reasonable causal relationship to a medicinal product qualify as adverse reactions.

**Unexpected adverse reaction**: an adverse reaction, the nature or severity of which is not consistent with the applicable product information i.e. the summary of product characteristics (SPC).

**A serious adverse event or serious adverse reaction**: any untoward medical occurrence or effect that at any dose fulfils at least one of the following criteria:

- results in death
- is life-threatening
- requires inpatient hospitalisation or prolongation of existing hospitalisation
- results in persistent or significant disability/incapacity

**Or**

- is a congenital anomaly/birth defect

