### Procedure

- Document the event on the adverse event form. Keep a copy of adverse event form (1) (see appendix 3) in the trial file within 7 days of first being aware of the adverse event.
- Document in a clear way as far as possible. For example, the patient may say that they 'felt sick'. This can be interpreted in many ways: either they felt nauseated or they may have felt unwell, or they may even have been vomiting.
- Ask patient the date and start and stop time of event. If the patient cannot remember, then as near as possible.
- Document the action taken regarding study drug e.g. was the treatment dose reduced, or was study drug/treatment delayed etc.
- Document any treatment/medication given for the event, including the dates the treatment/medication was commenced and the date it was stopped/changed, if applicable.
- Document the event outcome.
- Document the seriousness (see the above definition of what is a serious event).
- Grade the adverse event using the National Cancer Institute's Common Terminology Criteria for Adverse Events v3.0 (CTCAE)
- Document the causality. Does the adverse event have a reasonable suspected causal relationship with doxycycline?
- The relationship of adverse events to the products being studied should be determined according to the five categories classification below. Of the five, "possibly", "probably" and "definitely" related to an investigational medicinal product qualify as adverse reactions; "unlikely" and "not related" would not qualify as a reasonable causal relationship.

**Not related** - temporal relationship of the onset of the event, relative to administration of the product, is not reasonable or another cause can by itself explain the occurrence of the event.

**Possibly related** - temporal relationship of the onset of the event, relative to administration of the product, is reasonable but the event could have been due to another, equally likely cause.

**Probably related** - temporal relationship of the onset of the event, relative to administration of the product, is reasonable and the event is more likely explained by the product than by another cause.

**Definitely related** - temporal relationship of the onset of the event, relative to administration of the product, is reasonable and there is no other cause to explain the event.

- Document the expectedness (see the above definitions of an expected and unexpected event).

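### The call list under Table 2 omits months 1 and 2, when the first two dose increases occur, although the protocol's own call rule covers them

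*Protocol*

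**What the plan says.** Three parts of the protocol bear on this point.

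**Dose.** Patients start on 50 mg once daily. The section Dose escalation of doxycycline and urine zymography then says: "After one month doxycycline will be increased from 50mg od to 50mg bd, after two months to 50 mg tds", with 100 mg twice daily from month 3. It adds: "Patients will stay on this dose for the remainder of the study". An independent person adjusts the dose blind, and every patient takes four tablets throughout. Urine at months 1, 2 and 3 is posted to the centre.

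**Safety contact.** At week 2, on the starting dose: "After two weeks of doxycycline treatment patients will have a safety screen comprising FBC, U&E, LFT, glucose, and amylase", together with a phone call. From month 3 patients attend every three months (Routine study assessments): "For safety purposes patients will have urinalysis, FBC, U&E, LFT, glucose, amylase and a pregnancy test". Between visits, Monthly phone contact says: "During months when no study visit is scheduled a telephone call will be made to participants to check compliance". The same sentence gives repeating the safety advice and finding adverse events as further purposes.

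**Call list.** The note under Table 2 reads: "A study phone call will take place at 2 weeks, 4, 5, 7, 8, 10, 11,13, 14". It continues with months 16, 17, 19, 20, 22 and 23. Months 1 and 2 are not in it.

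**The concern.** The call rule and the call list disagree, and they disagree only in the two months when the dose is being raised between visits. A schedule table is what site staff usually work from. If they do so here, the first two increases are made without anyone being scheduled to ask the patient about adverse events.

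Defining the safety profile of doxycycline and finding the dose that suppresses MMPs are both stated aims. Calls at months 1 and 2 would give the tolerability and compliance data for the 50 and 100 mg/day steps, which are the doses at which those urine samples are taken.

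A smaller gap sits beside this one. The escalation text depends on time alone, while the section Management of adverse events associated with doxycycline allows treatment to be interrupted. After a significant photosensitivity reaction, for example, treatment stops for a week and restarts at the unchanged dose. If that week spans a planned increase, the protocol does not say which instruction governs. Nor is there a rule for an abnormal blood result, although the adverse event definition includes "any unfavourable and unintended sign (including an abnormal laboratory finding), symptom or disease temporally associated with the study drug".

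**Working it through.** **1. Calls required against calls listed.**
- Study visits (Routine study assessments): months 3, 6, 9, 12, 15, 18, 21, 24, which is 8 months.
- Months without a visit: 24 - 8 = 16, namely 1, 2, 4, 5, 7, 8, 10, 11, 13, 14, 16, 17, 19, 20, 22, 23.
- Monthly calls listed under Table 2: 4, 5, 7, 8, 10, 11, 13, 14, 16, 17, 19, 20, 22, 23, which is 14 calls (plus the 2-week call).
- Required but not listed: months 1 and 2. Listed but not required: none.

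**2. Could months 1 and 2 count as visits?** Table 2 heads its columns as visits and includes both months. The only item ticked there is urine zymography, and that urine is posted. History and examination, bloods, urinalysis, pregnancy test and epilepsy review are all unticked. Even if these months are called visits, no safety enquiry is scheduled in them.

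**3. Length of the gap.**
- One month = 365.25 / 12 / 7 = 4.35 weeks; three months = 13.04 weeks.
- Following the Table 2 list, week 2 to month 3: 13.04 - 2 = 11.04 weeks.
- After month 3, visits and listed calls together cover every month, so the longest gap is 4.35 weeks. Ratio: 11.04 / 4.35 = 2.5.
- Following Monthly phone contact, the early gaps are 4.35 - 2 = 2.35 weeks, then 4.35 and 4.35 weeks.

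**4. Dose increases inside the gap.** Daily doses are 50 mg, then 2 x 50 = 100 mg, then 3 x 50 = 150 mg, then 2 x 100 = 200 mg. The first two of the three increases fall between week 2 and month 3. The third coincides with the month 3 visit and its bloods.

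**5. How many patients might meet an event at a step?** The protocol cites photosensitivity in about 8 to 11% of users and oesophagitis in about 4%. If those rates applied to the 20 patients planned for doxycycline, this would be 20 x 0.08 = 1.6 to 20 x 0.11 = 2.2 patients, and 20 x 0.04 = 0.8 patients. The timing is not given, so fewer would coincide with an increase. No rate is given for blood abnormalities, and none is assumed.

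**The case against.** The strongest reply is that Monthly phone contact is the procedure text and already requires both calls. The 11-week gap then arises only for staff who follow the note to a data capture table instead. That is correct, and it limits the point to a contradiction to be removed. It does not dispose of it, because the note is an explicit list of call dates and nothing says which text prevails.

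A reader might infer that escalation has no safeguards, or that a doctor could not hold a step. The documents do not support this. The section on managing adverse events gives interruption or withdrawal rules for gastrointestinal, skin, dental and yeast problems, and these apply at any time. The reporting procedure foresees changes to dosing: "Document the action taken regarding study drug e.g. was the treatment dose reduced, or was study drug/treatment delayed etc". Patients also have a 24-hour hotline and are encouraged to report events when they occur.

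A reader might also infer that each step needs a formal release decision for every patient, or that laboratory monitoring is thin. Neither follows. The protocol gives the usual adult dose as 100 to 200 mg/day, so the trial starts below that range and never exceeds it. The first three months contain two on-treatment blood sets (week 2 and month 3), against one in each later quarter. Step-by-step release would mean 3 x 40 = 120 record reviews, and the second increase would still rest on bloods taken at 50 mg/day. It is a preference, and it could cost MMP data at the higher doses.

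**Conclusion.** The point stands as a minor safety correction. The call list contradicts the call rule at months 1 and 2 and nowhere else. Read literally, the list leaves about 11 weeks without scheduled safety contact while the dose rises from 50 to 150 mg/day; under the call rule the longest gap is 4.35 weeks. Alongside this, the escalation text does not say what happens at a planned increase when a patient is interrupted, is being managed for an adverse event or has an unresolved blood abnormality.

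Few patients are likely to be affected, and no probability of harm is claimed. The 11-week figure assumes that staff follow the list under Table 2. The mismatch itself is certain. The remark about the missing hold rule concerns the visible text only, because some pages between the section on managing adverse events and Patient contacts are not in the public copy.

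**What to change.** **Call list.** Add months 1 and 2 to the note under Table 2, with each call made before that month's increase.

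**Escalation section.** Add one sentence: an increase is not made while a patient is interrupted or being managed for an adverse event under the section on managing doxycycline adverse events, or has an unresolved, clinically significant abnormality on the latest available safety bloods. Such a patient stays at the current step. The rule is the same in both arms and is applied blind. The sentence fixing the final dose should be qualified so that a held patient remains on the highest step reached. The Summary, which leaves out the three-times-daily step, can be aligned in the same amendment.

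**Cost.** The calls number 2 x 40 = 80, all already required by Monthly phone contact. No test or visit is added. The four-tablet scheme can conceal a held step, but the protocol does not describe how packs are supplied, so dispensing may need a small adjustment. The third increase may have to wait for the month 3 results. A few held patients may contribute no MMP data at the higher doses; each one on doxycycline is 1 of 20, or 5% of that arm.

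### On the detailed escalation schedule, urine MMPs are read one month into each lower dose, but the dose held for 21 of 24 months is first read nine months after it starts

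*Protocol*

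**What the plan says.** The first stated aim (Protocol, section 2) is to "determine the optimum dose of doxycycline needed to suppress MMP production". The Summary also lists the dose required to suppress MMP activity among the main endpoints.

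The schedule is set in section 3:

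- **Start:** "Patients will be randomised to either doxycycline 50 mg od or matched placebo".
- **Purpose of the escalation:** "In order to determine the dose of doxycycline that suppresses MMP production doxycycline will be increased and urine MMPs measured".
- **First step:** "After one month doxycycline will be increased from 50mg od to 50mg bd".
- **Second and third steps:** "after two months to 50 mg tds and at three months to 100 mg bd. Patients will stay on this dose" until the end of the study.
- **Sampling:** "At one, two and three months urine will be sent by post to the study centre".

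In Table 2 (data capture summary) the row "Urine zymography" is ticked at screening and at months 1, 2, 3, 12 and 24, with nothing at months 6 or 9. Serum MMPs are ticked only at screening and months 12 and 24.

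The Summary gives the order of sample and step, with increases made "at monthly intervals up to three months after urine zymography has been performed". The same sentence describes a two-step escalation, from 50 mg bd straight to 100 mg bd, without the 50 mg tds step.

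The Dosage paragraph in section 4 says only that data relating doxycycline to serum and urine MMPs will be presented.

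**The concern.** The month 1, 2 and 3 urines exist to show which dose suppresses MMPs. On the detailed schedule they cover three of the four dose levels, each after the same interval. The fourth level, on which patients spend most of the trial and which therefore drives the efficacy result, has no matching reading.

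Suppose MMPs are present at month 3 and absent at month 12. The data could not say whether the last dose increase or the longer exposure was responsible.

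Losses add to this. Under the combined safety endpoint, placebo patients who decline may be unblinded and offered doxycycline, and patients with pneumothorax, increasing chylous effusion or a bleeding angiomyolipoma are withdrawn. Section 4 continues measurements after withdrawal where possible, but urine taken off drug is not a final-dose reading, and urine from a placebo patient who has started doxycycline is not a placebo reading. These losses would tend to fall on patients with more active disease.

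**Working it through.** The plan states no figure to reproduce here; the check is a timeline.

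**Inputs.** Dose steps at months 0, 1, 2 and 3 (section 3, randomisation and dose-escalation paragraphs). Urine at months 1, 2, 3, 12 and 24 (Table 2). Sample before step (Summary; the dose-escalation paragraph does not state the order). Follow-up of 24 months.

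**Formula.** Months on current dose = sample month − month of the last step before the sample. Time on drug = sample month.

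| Urine (month) | Daily dose read | Months on that dose | Months on drug |
|---|---|---|---|
| 1 | 50 mg | 1 − 0 = 1 | 1 |
| 2 | 100 mg | 2 − 1 = 1 | 2 |
| 3 | 150 mg | 3 − 2 = 1 | 3 |
| 12 | 200 mg | 12 − 3 = 9 | 12 |
| 24 | 200 mg | 24 − 3 = 21 | 24 |

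The final dose runs 24 − 3 = 21 months, or 21/24 = 88% of follow-up. Between successive early samples, time on drug grows by one month. Between the 150 and 200 mg/day readings it grows by 12 − 3 = 9 months.

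**The same check on the Summary's two-step escalation.** The Summary does not fix the month of the second step, so both readings are shown.

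| Reading of the Summary | Month 3 urine reads | First 200 mg/day urine | Months on final dose |
|---|---|---|---|
| Steps at months 1 and 2 | 200 mg/day after 1 month | Month 3 | 24 − 2 = 22 |
| Steps at months 1 and 3 | 100 mg/day after 2 months | Month 12, after 9 months | 24 − 3 = 21 |

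On the first reading the gap disappears; on the second it remains.

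**Losses.** The documents give no withdrawal rate. If 10–20% of 20 doxycycline patients left between month 3 and month 12 (an assumption), 0.10 × 20 = 2 to 0.20 × 20 = 4 would have no on-drug final-dose reading. This is an upper bound on what an added sample could recover, because anyone who left before that sample would still be missed.

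**Assay count.** Six urines × 40 patients = 240 planned. One more per patient adds at most 40, and 40/240 = 17%.

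**The case against.** The strongest objection is that the final dose is measured, and measured twice. Table 2 applies to both arms, so placebo urine exists at months 12 and 24. A between-arm contrast there removes calendar time and disease progression. A reader might infer that the 200 mg/day result is confounded with nine months of progression, or that suppression first occurring at that dose could not be seen at all. The documents support neither. Progression would bias only a within-arm comparison of month 12 with the earlier months, and MMPs present at month 3 but suppressed relative to placebo at month 12 would be visible. What remains is that the data cannot separate dose from duration of exposure.

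Second, forced titration ties dose to time on drug at every step, so an extra sample cannot break the link. That is correct. A month 4 urine would read 200 mg/day after four months on drug, against three months for 150 mg/day. It makes the last step comparable with the earlier ones and does no more. A month 6 urine would come three months after the step and matches less well.

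Third, the Summary's escalation differs, and on one reading the month 3 urine is already a one-month reading of the final dose. This objection stands, and it makes the point conditional. It matters the more because the order of sample and step is taken from the same sentence of the Summary.

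Fourth, MMPs are in neither the primary nor the listed secondary endpoints, no test is planned, zymography does not decide anyone's dose, and the trial is meant to be simple and inexpensive. This limits the weight of the point but does not remove it, since the suppressing dose is aim 1 and a main endpoint in the Summary.

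**Conclusion.** The point holds conditionally and is of moderate weight. On the detailed escalation paragraph and Table 2, with samples taken before each step, three dose levels are read after one month each, and the level held for 21 of 24 months is first read after nine. The month 12 and 24 contrasts with placebo are sound for calendar time and progression. They cannot separate the final dose from much longer exposure, and they lose a clean comparison for patients who withdraw or cross over before month 12.

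The conclusion depends on which escalation applies; if the Summary's steps fall at months 1 and 2, it does not arise. A reader might also infer that the efficacy result is compromised. It is not: the FEV1 slope comparison, its power and the safety analyses do not use these samples. The supplementary results at the end of the document report what was done and do not alter what the plan specifies.

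**What to change.** 1. Reconcile the escalation in the Summary with that in section 3, and state in section 3 whether each urine is taken before the dose step.
2. If the section 3 schedule stands, add one urine zymography in both arms about one month after the last step, at month 4, and tick it in Table 2. The postal route is already in use and a month 4 telephone call is already scheduled. As a less closely matched fallback, assay the urine already collected for urinalysis at the month 6 visit.
3. In the Dosage paragraph of section 4, specify that each dose is compared with placebo urine from the same time point, that months 12 and 24 serve to show durability, and that forced titration still ties dose to cumulative time on drug.

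The cost is at most 40 zymograms on about 240 planned. No visit is added, and no collection is added if the month 6 urine is used. Dosing and the primary analysis stay as they are. The sample has to be scheduled in the protocol, because later analysis cannot recover a urine that was never assayed.
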